5.1.3. Storage and stability of study drugs

The investigator, or his/her authorized representative (e.g., pharmacist), will ensure that all study drugs are stored in a secure area with controlled access, in compliance with storage conditions, and in accordance with applicable regulatory requirements.

The investigational drug should be stored in its original container and as indicated on the drug label. If the storage conditions on the label and in other materials of the investigational drug (such as the Pharmacy Manual) are inconsistent, the storage conditions on the label shall prevail.

The study site must be able to measure and record the daily maximum and minimum temperatures at all storage locations (such as frozen, refrigerated, or room temperature). The recording period should start from the receipt of the investigational drug until the end of the study. Even with continuous monitoring system in place, the study site should maintain a record log to ensure proper storage temperatures. Temperature monitoring devices and storage devices (such as refrigerators) should be regularly inspected to ensure proper functioning.

Once any deviation from the conditions on product label occurs, it should be reported promptly upon discovery. The investigator should actively take measures to return the investigational drug to the storage conditions described on the label as soon as possible. Meanwhile, the temperature deviation and the measures taken should be reported to the sponsor.

Investigational drugs affected by temperature deviations must be temporarily separated until permission is granted by the sponsor to continue their use, and this will not be considered as a protocol deviation. If the affected investigational drugs are used without the sponsor's permission, it is considered a protocol deviation. The sponsor will provide the study site with specific procedures for reporting temperature

deviations.

5.1.4. Preparation of study drugs

SHR-1210 should be prepared by qualified or experienced investigators, such as physicians, pharmacists, or medical assistants (as permitted by national or institutional operating guidelines), based on the pharmacy manual and package insert of commercially available drugs. For the mixing method and concentration (preparation) of the dosing solution and its usage, please refer to the SHR-1210 Pharmacy Manual. Since this product does not contain any preservatives or antimicrobial agents with antimicrobial activity, it is essential to be cautious and ensure that the prepared solution is sterile.

The total storage period for prepared SHR-1210 solution (total time stored in the refrigerator and at room temperature) must not exceed 24 hours after preparation. For detailed information on the storage and use time of the prepared drug solution at room temperature/light exposure and in the refrigerator, please refer to the Pharmacy Manual. Expired or remaining drug solution must be discarded.

5.1.5. Method of use of study drugs

SHR-1210 is an intravenous injection, which must be administered by qualified or experienced study personnel in the outpatient department or ward of the study site. It is not allowed to be taken out of the study site for use.

Within 72 hours prior to each administration, except for imaging examinations, the subjects must complete all necessary clinical examinations to assess the tolerability of further medication use.

SHR-1210 will be administered via intravenous infusion for 30 minutes (not less than 20 minutes and not more than 60 minutes, including the flushing phase).

Intravenous and rapid bolus injections should not be allowed.

Intravenous will be performed through a medical infusion bag using an infusion set with an inline filter (0.2 µM).

Before and after the infusion, do not administer other medications through the infusion pathway.

Apatinib mesylate tablets are an oral formulation. The investigator will prescribe them for the patients, who will be responsible for obtaining their own supply. The tablets should be taken orally after a meal, as detailed in the dosing regimen.

5.1.6. Precautions for special dosing equipment

The study site must also obtain intravenous infusion bags, diluents, and micron-level filters in the infusion lines (i.e., 0.2/1.2 µm); the required filters are detailed in the Pharmacy Manual.

5.2. Dosing regimen

SHR-1210 will be administered via intravenous infusion (no prophylactic medication required) at a fixed dose of 200 mg, and 3 mg/kg for patients weighing < 50 kg at baseline. Each infusion will last for 30 minutes (no less than 20 minutes, no more than 60 minutes), and the drug will be administered once every 2 weeks, with 4 weeks for one cycle and the maximum cumulative treatment duration of 2 years.

During the study period, SHR-1210 will be administered once every 2 weeks, with a dosing window of ±3 days from the scheduled dosing time. If the administration of SHR-1210 is delayed by more than 3 days from the scheduled dosing time, the dose will not be given for that time, and the original dose will be given at the next scheduled dosing time.

Apatinib will be taken orally after a meal, once daily, with 2 tablets per dose (250 mg per tablet). The dose of apatinib will be adjusted according to the patient's tolerance, with continuous administration and 4 weeks for one cycle.

Definition of "Administration after a meal": Administration within 30 minutes of the end of meal.

Patients will receive the investigational drug until the treatment discontinuation criteria specified in the protocol are met.

5.3. Dose modifications

During the study period, dose modifications of the investigational drug can be made based on its toxic side effects, including: dose interruption, dose reduction, modification of administration mode, and dose termination.

Dose interruption is allowed for SHR-1210, with a maximum allowable drug interruption of 12 weeks.

In addition to dose interruption, for subjects whose weight decreases to below 50 kg during the treatment period, the dose of SHR-1210 may be down-titrated to 3 mg/kg q2w, as appropriate.

Dose modifications due to apatinib-related toxicity include: dose interruption, dose reduction, modification of administration mode (first modification: 5 days on treatment and 2 days off; second modification: 7 days on treatment and 7 days off), and dose termination. During the study, after adjusting the administration mode of apatinib, the recovery of dose mode will not be allowed.

During the study, if definite apatinib-related AEs occur, such as hypertension, proteinuria, hand and foot syndrome (HFS), apatinib administration may be down-titrated or interrupted. After toxicity recovery, the original dose, adjusting the administration method, or terminating the dose may be given as appropriate. After discontinuing apatinib, the study subjects may continue to receive SHR-1210 monotherapy.

During the study, if immune-related toxicities occur, such as immune pneumonia,

hepatitis, enteritis, the administration of SHR-1210 and apatinib should be suspended as appropriate. Once the toxicity has recovered to \leq grade 1 or baseline levels (for the increase of laboratory parameters such as ALT/AST and total bilirubin [TBIL]), the medication can be resumed. The administration of SHR-1210 should be resumed first, and after 14 days of observation without significant abnormalities, the administration of apatinib can be initiated and the mode of subsequent administration of apatinib will be adjusted.

During the study, if \geq grade 3 immune pneumonia, \geq grade 3 TBIL increased, grade 4 ALT/AST increased, or other grade 4 immune-related toxic reactions, grade 4 injection reactions occur, or if the immune-related toxicity causes a temporary suspension of SHR-1210 administration for more than 12 weeks and still cannot recover to \leq grade 1 or baseline level, SHR-1210 must be permanently discontinued.

During the study, if \geq grade 3 capillary hyperplasia occurs, no dose modifications are required for apatinib, and SHR-1210 should be suspended until the toxicity recovers to \leq grade 2.

During the study, if the subject exhibits abnormal symptoms/signs or laboratory indicators, symptomatic treatment should be taken promptly, and it is recommended to refer to the following table for corresponding dose modifications:

Table 1 Dose Modifications

Drug-related Toxicity		Grading	Dose Interrupted or Not		Criteria for Resumption of Dosing	Dose Modification Methods for Apatinib	Discontinuation Criteria
			SHR-1210	Apatinib			
SHR-1210 and apatinib-related toxicities	Hematologic toxicity	Grade 1 and 2	No	No	-	-	-
		Grade 3	Yes	Yes	When toxicity recovers to \leq grade 2	Original dose	After two modifications, if \geq grade 3 hematologic toxicity occurs again, the administration of apatinib will be terminated.
	Grade 4	Yes	Yes	When toxicity recovers to \leq grade 2	First modification: Adjust to 5 days on treatment and 2 days off; Second modification: Adjust to 7 days on treatment and 7 days off;		
	Immune-related	Grade 2	Yes	No	When toxicity recovers	First modification: Resume	Unable to recover to \leq grade

Drug-related Toxicity	Grading	Dose Interrupted or Not		Criteria for Resumption of Dosing	Dose Modification Methods for Apatinib	Discontinuation Criteria
		SHR-1210	Apatinib			
ated pneumonia				to ≤ grade 1	at original dose Second modification: Adjust to 5 days on treatment and 2 days off; Third modification: Adjust to 7 days on treatment and 7 days off	1 after > 12 weeks of discontinuation
ALT/AST and TBIL increased (after receiving	Grade 2 ALT or AST increased Grade 2 bilirubin	Yes	Yes	When toxicity returns to baseline	First modification: Adjust to 5 days on treatment and 2 days off; Second modification: Adjust to 7 days of on treatment	1. If discontinuation of the drug for >12 weeks still does not result in recovery to baseline levels, then terminate the use of

Drug-related Toxicity	Grading	Dose Interrupted or Not		Criteria for Resumption of Dosing	Dose Modification Methods for Apatinib	Discontinuation Criteria
		SHR-1210	Apatinib			
hepatoprotective treatment)	increased				and 7 days off;	SHR-1210.
	Grade 3 ALT / AST increased	Yes	Yes	When toxicity returns to baseline	First modification: Adjust to 7 days on treatment and 7 days off; Second modification: Permanently discontinue apatinib	1. If discontinuation of the drug for >12 weeks still does not result in recovery to baseline levels, then terminate the use of SHR-1210. 2. If grade 3 ALT/AST increased occurs again, then terminate the use of

Drug-related Toxicity	Grading	Dose Interrupted or Not		Criteria for Resumption of Dosing	Dose Modification Methods for Apatinib	Discontinuation Criteria
		SHR-1210	Apatinib			
						SHR-1210.
Other nonhematologic toxicities	Grade 1	No	No	-	-	-
	Grade 2 (lasting for \geq 7 days)	Yes	Yes	When toxicity recovers to \leq grade 1	Original dose	Unable to recover to \leq grade 1 after > 12 weeks of discontinuation
	Grade 3	Yes	Yes	When toxicity recovers to \leq grade 1	First modification: Adjust to 5 days on treatment and 2 days off; Second modification: Adjust to 7 days on treatment and 7 days off;	
SHR-1210 Capillary	Grade 3	Yes	No	When toxicity recovers	Original dose	> 12 weeks of SHR-1210

Drug-related Toxicity		Grading	Dose Interrupted or Not		Criteria for Resumption of Dosing	Dose Modification Methods for Apatinib	Discontinuation Criteria
			SHR-1210	Apatinib			
-related toxicities	hemangioma				to ≤ grade 2		discontinuation
Apatinib-related toxicities	Hypertension	Grade 3 (After corrective treatment)	No	Yes	When toxicity recovers to ≤ grade 1	
First modification: Resume at original dose
 
Recurrent grade 3 hypertension: Adjust to 5 days on treatment and 2 days off for apatinib.
 
The third occurrence of grade 3 hypertension: Adjust to 7 days on treatment and 7 days off for apatinib.
	After two modifications, grade 3 hypertension occurs again, and the administration of apatinib will be terminated.

Drug-related Toxicity	Grading	Dose Interrupted or Not		Criteria for Resumption of Dosing	Dose Modification Methods for Apatinib	Discontinuation Criteria
		SHR-1210	Apatinib			
	Hypertensive crisis	Yes	Yes	When toxicity recovers to \leq grade 1	Permanently discontinue apatinib	Discontinue apatinib
Proteinuria (Without significant increase in blood creatinine)	Grade 3 (24-h urine protein quantitation)	No	Yes	When toxicity recovers to \leq grade 2	Adjust to 5 days on treatment and 2 days off for apatinib; Recurrence of grade 3 proteinuria: Adjust to 7 days on treatment and 7 days off for apatinib.	After two modifications, grade 3 proteinuria occurs again, and the administration of apatinib will be terminated.
Hand and foot syndrome	Grade 3	No	Yes	When toxicity recovers to \leq grade 1	Adjust to 5 days on treatment and 2 days off for apatinib; Recurrence of	After two modifications, grade 3 hand and foot syndrome occurs again, and

Drug-related Toxicity	Grading	Dose Interrupted or Not		Criteria for Resumption of Dosing	Dose Modification Methods for Apatinib	Discontinuation Criteria
		SHR-1210	Apatinib			
					grade 3 hand and foot syndrome: Adjust to 7 days on treatment and 7 days off for apatinib.	the administration of apatinib will be terminated.
Headache	After symptomatic treatment, the duration of grade 2 headache is ≥ 7 days, or grade 3	No	Yes	When toxicity recovers to \leq grade 1	Adjust to 5 days on treatment and 2 days off for apatinib; Recurrence: Adjust to 7 days on treatment and 7 days off for apatinib	Recurrence after two modifications, discontinue apatinib

Drug-related Toxicity	Grading	Dose Interrupted or Not		Criteria for Resumption of Dosing	Dose Modification Methods for Apatinib	Discontinuation Criteria
		SHR-1210	Apatinib			
	headache					

During the study, if a subject experiences significant toxicity that persists after symptomatic treatment, including grade 2 non-hematologic toxicity lasting for 2 weeks or more (excluding asymptomatic grade 2 hypertension) and abnormal laboratory test results (excluding proteinuria < 2 g/24 h), the investigator may consider, based on the subject's tolerance, to temporarily discontinue the medication and, after toxicity recovery, to choose a reduced dose of apatinib or adjust the administration mode of apatinib in subsequent study stages.

During the study, the investigator may make appropriate dose modifications in accordance with the above-mentioned dose modifications, taking into account the occurrence of drug-related toxicities in the subjects. For example, if a subject experiences multiple grade 2 drug-related toxicities and has poor tolerance to the study drug, the investigator may adjust the administration mode or reduce the dose of apatinib after temporarily discontinuing the drug and the toxicities have resolved.

During the study, if a subject experiences fever (> 38°C, requiring corrective treatment), or significant symptoms of gasping, polypnoea, breathlessness, the administration of SHR-1210 will not be given at the current or next scheduled dose time until the symptoms have resolved. After the symptoms have relieved and stabilized for more than 7 days, the administration of SHR-1210 will be resumed according to the subsequent planned schedule. If necessary, pneumonia should be ruled out by imaging examination before administration.

During the study period, if any of the following occurs: hypertensive crisis, hemorrhage brain, \geq grade 2 pulmonary hemorrhage, \geq grade 3 other hemorrhages, arterial thrombosis, grade 4 venous thrombosis, leukoencephalopathy syndrome, or gastrointestinal perforation, the administration of apatinib should be terminated, and the administration of SHR-1210 should be suspended. Active symptomatic treatment

should be provided, and the decision to continue SHR-1210 treatment will be based on the recovery status of the toxicity in the subject.

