10.1. Sample size

This study is a single-arm study, with the primary efficacy endpoint being ORR. It is planned to enroll 30 patients.

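### Read literally, Table 1's apatinib steps conflict with the no-return rule in section 5.3 and, for hypertension, with the row's own stop criterion

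*Protocol*

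**What the plan says.** Protocol section 5.2 starts apatinib at two 250 mg tablets once daily, taken continuously. Section 5.3 lists interruption, dose reduction, change of mode and termination as separate responses to apatinib toxicity. It numbers the mode changes as "first modification: 5 days on treatment and 2 days off; second modification: 7 days on treatment and 7 days off" (below, 5/2 and 7/7) and adds that "after adjusting the administration mode of apatinib, the recovery of dose mode will not be allowed". Neither statement is limited to a particular toxicity.

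Table 1, which follows and is introduced as recommended, sets the steps row by row:

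- **Proteinuria, grade 3:** "Adjust to 5 days on treatment and 2 days off for apatinib; Recurrence of grade 3 proteinuria", with 7/7 attached to that recurrence. The hand and foot syndrome (grade 3) and headache rows have the same pattern. In all three, apatinib stops if the same toxicity returns after two modifications.
- **Hypertension, grade 3:** the first event reads "First modification: Resume at original dose", and the second gives 5/2. Then: "The third occurrence of grade 3 hypertension: Adjust to 7 days on treatment and 7 days off for apatinib". The stop cell reads: "After two modifications, grade 3 hypertension occurs again, and the administration of apatinib will be terminated".

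Several rows use the term 'original dose'. The protocol does not define it for a patient whose mode has already been changed.

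**The concern.** Section 5.3 reads as a single one-way sequence, whereas three rows of Table 1 name a fixed first step whatever mode the patient is already on. The two agree for a patient with one toxicity. They part once a patient already on a changed mode has a different one. Section 5.3 itself names hypertension, proteinuria and hand and foot syndrome as examples of apatinib-related events, so such a patient is foreseeable.

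The hypertension row raises a separate problem that needs no second toxicity. It calls resumption a modification, while 5.3 starts counting at 5/2, and its stop criterion depends on the count.

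At stake are apatinib exposure after a further toxicity, the event at which apatinib ends, and a listed secondary safety endpoint, the rate of dose discontinuation for adverse events.

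**Working it through.** The protocol gives no figure to reproduce. The check converts each mode to an average weekly amount and then follows the rows literally.

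**Inputs.** 500 mg per dosing day (section 5.2); modes 5/2 and 7/7 (section 5.3); row instructions (Table 1); sample size, "It is planned to enroll 30 patients" (section 10.1).

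**Average weekly apatinib** = 500 mg × days on ÷ weeks in the pattern.

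- Continuous: 500 × 7 = 3500 mg
- 5/2: 500 × 5 = 2500 mg (2500/3500 = 71%)
- 7/7: 500 × 7 ÷ 2 = 1750 mg (1750/3500 = 50%)

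**Two toxicities, patient on 7/7.** Two grade 3 hand and foot events lead to 5/2 and then 7/7. A first grade 3 proteinuria follows, and its row says 5/2. The change is 2500/1750 = 1.43, or +43%, and 5.3 does not allow it. Suppose instead that 5.3 prevails. The row's first step is then barred, its second step needs a recurrence of proteinuria, and its stop cell needs proteinuria to return after two modifications. None of these fits a first proteinuria event, and no other passage says what does.

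**Two toxicities, patient on 5/2.** One grade 3 hand and foot event leads to 5/2. A first grade 3 proteinuria again gives 5/2, so exposure stays at 2500 mg/week. If the 5.3 sequence is counted across toxicities, the next step is 7/7, or 1750 mg/week.

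**Hypertension row alone.**

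| Grade 3 event | Modification cell | Count by the row's label | Count by 5.3 |
|---|---|---|---|
| 1st | original dose | first | none |
| 2nd | 5/2 | second | first |
| 3rd | 7/7 | two already made: stop cell met | second |
| 4th | none given | – | two already made: stop cell met |

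The third event therefore gives 1750 mg/week or 0, depending on which numbering is used.

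**'Original dose'.** If it means 500 mg every day, a patient on 5/2 would go up by 3500/2500 = 1.40 (+40%) and one on 7/7 by 3500/1750 = 2.00 (+100%). If it means the tablet dose with the current mode kept, the change is zero.

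**Endpoint.** If all 30 patients enter the safety set and apatinib termination counts towards the discontinuation rate, each patient counted differently moves that rate by 1/30 = 3.3 percentage points.

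**The case against.** A reader might infer that the protocol tells investigators to raise apatinib after a second type of toxicity. The documents do not support that. The no-return sentence is unqualified, Table 1 is only recommended, and 5.3 lets the investigator change the mode or reduce the dose in view of the patient's toxicities. Read together, these can block the move from 7/7 to 5/2. Nor does any passage say outright that the sequence restarts for each toxicity. This part of the objection stands, but it leaves the gap: once the row's step is barred, nothing replaces it.

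Other stronger readings also fail or stay conditional:

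- **A return to daily dosing.** The +40% and +100% figures hold only on one meaning of 'original dose'. For grade 3 capillary hyperplasia the text says apatinib needs no modification, and the matching row says 'original dose', which suggests no change.
- **An increase straight after the event.** The proteinuria, hand and foot and headache rows first interrupt apatinib until recovery to the stated grade.
- **'Two modifications' has no common meaning because the pneumonia and grade 3 ALT/AST rows differ.** Those rows do not use that stop criterion, so they cannot show it.
- **Variation between sites.** The trial is single-center; any variation would be between investigators or between patients.

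On hypertension, the fair reply is that this is a labelling slip. The row expressly gives 7/7 at the third event, and stopping there would empty that instruction, so the fourth event is the more coherent reading. That has force. The label still stands in the row, and the pneumonia row likewise numbers resumption as its first modification, so an investigator who counts by the table's labels has grounds for doing so.

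**Conclusion.** The point holds as two conflicts in wording within section 5.3. In the proteinuria, hand and foot syndrome and headache rows, a patient already on 7/7 is directed to a mode that 5.3 bars (+43% in average weekly apatinib), and a patient already on 5/2 gets no further step. In the hypertension row, the third grade 3 event meets both a 7/7 instruction and, by the row's own label, the stop criterion. The undefined 'original dose' is a further ambiguity whose size runs from zero to +100%, depending on its meaning.

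This rests on reading the rows literally and on 500 mg per dosing day with no separate dose reduction. The documents give no frequency for patients with two such toxicities, so the number affected cannot be estimated. The sample size and the ORR analysis are untouched. The statistical consequence is limited to a descriptive safety rate, but safety rules on exposure and termination should give one answer.

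**What to change.** Amend section 5.3 and Table 1 so that they agree:

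1. State whether apatinib modifications are counted across toxicities or per toxicity, and how that fits the no-return sentence, including for a patient already on 7/7 who has a first event of another kind.
2. Define 'original dose' for a patient on a changed mode.
3. Make the labels and stop cell of the hypertension row use the same numbering as 5.3, so that each event leads to one instruction.

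Which rule applies is for the sponsor's clinical team; this review proposes none. The cost is a wording amendment and a memo to the study site, with no extra patients or data.

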Therefore, when patients experience or report \geq grade 2 fatigue and weakness, it should be paid more attention to. If \geq grade 3 fatigue and weakness occur, patients should be admitted to the hospital immediately for examination. Potential causes, such as electrolyte disturbance, abnormal liver function, abnormal cardiac function (electrocardiogram, echocardiography), and abnormal hormone levels (adrenal hormones, thyroid hormones), should be considered and ruled out one by one. Symptomatic treatment should be provided, and according to the dose adjustment principles, the dose interruption or adjustment should be performed on the investigational drug accordingly.

7) Abdominal pain

Abdominal pain is not uncommon in apatinib treatment, often as a symptom associated with the tumor. Moreover, gastrointestinal perforation occasionally occurs in clinical studies of apatinib and other types of anti-angiogenic drugs. For patients experiencing abdominal pain, investigators should be vigilant for the possibility of gastrointestinal perforation. Once gastrointestinal perforation is identified, the medication must be stopped immediately, the patient should withdraw from the study, and active symptomatic treatment should be initiated.

8) Pulmonary interstitial fibrosis

Clinical physicians should have a thorough understanding of the patient's disease condition and be familiar with drugs that may cause pulmonary toxicity. The patient's clinical symptoms and changes in chest X-ray or CT scans should be closely

monitored. Once the patient experiences unexplained symptoms such as cough, chest tightness, breathlessness, difficulty breathing, and hemoptysis, it is crucial to promptly identify the cause and discontinue the medication as soon as other causes (such as infection and heart failure) are ruled out.

Bronchoalveolar lavage examination and surgical lung biopsy are important methods for diagnosing interstitial lung disease. Currently, there is no satisfactory treatment for pulmonary fibrosis. It is recommended to refer to the guidelines for the diagnosis and treatment of idiopathic pulmonary (interstitial) fibrosis issued by the Respiratory Diseases Branch of the Chinese Medical Association, correct hypoxemia, and drugs such as glucocorticoids should be used in a timely manner.

Note: Consult with a specialist if necessary to assist in diagnosis and treatment.

10. Data Analysis / Statistical Methods

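### For grade 2 immune-related pneumonia, the two apatinib cells of the Table 1 row do not match, and the row conflicts with the section 5.3 text on how apatinib is given afterwards

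*Protocol*

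**What the plan says.** Section 5.3 (Dose modifications) deals with immune-related pneumonia in two places.

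- **Text.** The immune-toxicity paragraph applies "if immune-related toxicities occur, such as immune pneumonia" and sets no grade for the hold. Its instruction reads "hepatitis, enteritis, the administration of SHR-1210 and apatinib should be suspended as appropriate". After recovery it continues: "The administration of SHR-1210 should be resumed first, and after 14 days of observation without significant abnormalities, the administration of apatinib can be initiated". It then adds that "the mode of subsequent administration of apatinib will be adjusted". An earlier paragraph of 5.3 makes any such change permanent: "after adjusting the administration mode of apatinib, the recovery of dose mode will not be allowed".
- **Table 1, immune-related pneumonia.** The only row is for grade 2. Its cells run "Grade 2 Yes No When toxicity recovers First modification: Resume" and then "at original dose Second modification: Adjust to 5 days on treatment and 2 days off; Third modification", the third step being 7 days on and 7 days off. The interruption columns are SHR-1210 first and apatinib second, so SHR-1210 is interrupted and apatinib is not.

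The text introduces Table 1 as a recommended reference, and the text after it lets the investigator adapt dose modifications to the toxicity seen. Section 9.1 mentions suspending SHR-1210 at grade 2 pneumonia and says nothing about apatinib.

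**The concern.** Two things do not fit together.

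First, inside the row, one cell says apatinib was not stopped and the next tells the site to resume it.

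Second, for a patient's first grade 2 event, the text provides for holding apatinib and, if it is held, a delayed restart in a changed mode. The table gives the original dose at that first event and reserves the mode change for the next one.

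Two patients with the same event could therefore receive different apatinib treatment, each in line with some part of the protocol. Immune-related pneumonia is a serious toxicity here: 5.3 stops SHR-1210 permanently at grade 3 or above. Because a mode change cannot be undone, the choice made at the first event also fixes the highest apatinib exposure the patient can have for the rest of treatment.

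**Working it through.** The protocol states no figure on this point, so the check is a comparison of text followed by simple arithmetic on exposure.

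**1. Is the row read correctly?** The column order can be tested on rows where the responsible drug is known. Grade 3 hypertension, listed as apatinib-related, reads No then Yes. Capillary hemangioma, listed as SHR-1210-related, reads Yes then No. So Yes then No in the pneumonia row means SHR-1210 held and apatinib continued. The mismatch does not come from a scrambled table.

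**2. Do the row's apatinib cells match?** In the hemangioma row, where apatinib is not interrupted, the modification cell says only that the original dose applies. In the hypertension row, where apatinib is interrupted, the first step is to resume at the original dose. The pneumonia row combines the interruption flag of the first pattern with the modification wording of the second.

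**3. Row against text, first grade 2 event**

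| Question | 5.3 text | Table 1 row |
|---|---|---|
| Apatinib held? | Yes, as judged appropriate | No |
| Timing of restart, if held | After SHR-1210 and 14 days of observation | Not stated |
| Apatinib afterwards | Mode adjusted, not reversible | Original dose; mode changes at the second step |

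The first line leaves room for judgement. The second is silence in the table, and matters only if apatinib was held. The third is a direct conflict once apatinib has been held.

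**4. Size, for a patient on 500 mg once daily**

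- Full schedule: 7 × 500 = 3500 mg per week.
- The immune-toxicity paragraph does not say which adjusted mode applies. I assume the sequence that 5.3 gives for apatinib-related toxicity. Its first change, 5 days on and 2 off, gives 5 × 500 = 2500 mg per week, and 2500/3500 = 71%. Its second, 7 on and 7 off, averages 3500/2 = 1750 mg per week, or 50%.
- The 14-day observation, if apatinib was held: 14 × 500 mg = 7 g. This needs no assumption about recovery time.
- Whole gap, if apatinib is held from onset: the length of the SHR-1210 hold plus 2 weeks. The protocol gives no recovery time. Assuming 4 weeks to grade 1 and 0 to 2 weeks to the next two-weekly SHR-1210 slot, the gap is 4 + (0 to 2) + 2 = 6 to 8 weeks, which is 42 to 56 doses (21 to 28 g). At the 12-week limit on SHR-1210 interruption it is 12 + 2 = 14 weeks, which is 98 doses (49 g). Under the table's No cell it is zero.

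**5. Endpoint.** The dose interruption rate due to AEs (synopsis; section 7.2.1) is not defined by drug. Table 1 interrupts SHR-1210 for this event, and so does the text where suspension is applied. A rate counted per patient would then include the patient either way. Only a rate reported for apatinib separately would differ.

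**The case against.** The strongest defence is that these passages were never meant as rigid rules. The suspension in 5.3 is left to what is appropriate and covers every immune-related toxicity at any grade, while the table is a recommended reference specific to grade. Read together, they could mean that at grade 2 pneumonia SHR-1210 is held and apatinib continues, which fits section 9.1. On that reading no restart sequence is needed. The row can still be followed: original dose at the first event, then the two mode changes. The word resume may simply have been carried over from the hypertension row.

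Much of this stands. A reader might infer that 5.3 requires both drugs to be stopped, or that the row cannot be carried out at all; the wording supports neither. The restart order is not a separate contradiction, since it arises only after a hold.

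Two things survive. The defence has to assume that one of the row's two cells is misworded, and the protocol does not say which. And if the investigator uses the discretion that 5.3 gives and holds apatinib, the text says its mode will be adjusted while the table says original dose. It could be argued that 500 mg on a 5-on/2-off schedule is still the original dose, but the table lists that schedule as a later and separate step.

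A reader might also cite section 9.4, item 8, as a third conflicting instruction. It concerns pulmonary interstitial fibrosis, and its instruction is to "discontinue the medication as soon as other causes (such as infection and heart failure) are ruled out". That is a different diagnosis with its own condition, and it contradicts neither passage.

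**Conclusion.** The point holds as an internal inconsistency confined to grade 2 immune-related pneumonia. The row's apatinib cells do not match each other. Where apatinib has been held, the row and the 5.3 text give incompatible instructions for a first event. The discretion in the wording softens the question of whether to hold apatinib; it resolves neither of these.

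Per affected patient, the lasting difference is 71% against 100% of the full weekly apatinib dose, assuming that the first adjusted mode is 5 days on and 2 off. The temporary difference is at least the 14 observation doses if apatinib was held; the 42 to 56 doses rest on the assumed 4-week recovery.

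A reader might go further and infer damage to the ORR or to the dose interruption endpoint. The protocol does not support that: it gives no expected number of such events among the planned 30 patients, and the interruption count changes only if it is reported for apatinib separately. The consequence is inconsistent handling of apatinib, and inconsistent exposure to it, during a serious toxicity. That is reason enough to correct the text.

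**What to change.** The sponsor's clinical team should reconcile three pieces of text: the 5.3 immune-toxicity paragraph, the apatinib interruption cell of the grade 2 pneumonia row, and the apatinib modification cell of that row. The agreed wording should say whether apatinib is held, in what order the two drugs restart if it is, and which dose or mode follows a first event. It should also state whether the text or the table governs if they differ. This review takes no view on which rule is right.

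The cost is amendment wording and notification of the site, with no added procedures or patients.
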